**Table 4: Implementation outcomes**

Outcomes	Definition as per McKay et al 2019 	Measurement tool
Reach	Proportion of the intended priority audience (i.e., participants) who participate in the intervention	Screening survey from recruitment website; baseline data form.
Adoption	Proportion and representativeness of providers or the delivery team that deliver an intervention	Study specific document maintained by trial manager; screening survey from recruitment website.
Fidelity	The extent to which an intervention is implemented as it was prescribed in the intervention protocol - by the delivery team	Study specific records
Dose (delivered)	Intended units of each intervention component delivered to participants by the delivery team	Study specific records
Determinants		
Acceptability (delivery team)	Perceptions among the delivery team that a given intervention is agreeable, palatable, or satisfactory	Qualitative interviews/ focus groups with delivery team
Acceptability (participants)	Perceptions among the participants that a given intervention is agreeable, palatable, or satisfactory	Includes 1. Study-specific documents on intervention components (e.g., agreement and participation in health coaching sessions); 2. data from message services on number who unsubscribe from messages, number messages opened; 3. Google analytics on website usage; 4. Engagement on Facebook; 5. Quantitative survey rating different elements of intervention; 6.

		Qualitative interviews with sub-group participants.
Cost	Money spent on design, adaptation, and implementation of an intervention	Study-specific log recording costs
Feasibility	Perceptions among the delivery team that an intervention can be successfully used or carried out within a given organisation or setting	Qualitative interviews/ focus groups with delivery team
Context	Aspects of the larger social, political, and economic environment that may influence intervention implementation	Field notes kept by Research Manager based on Consolidated Framework for Implementation Research (CFIR)
Adaptability	Extent to which an intervention can be adapted, tailored, refined, or reinvented to meet local needs	Study-specific document guided by expanded Framework for Reporting Adaptations and Modifications to Evidence-based interventions (FRAME) framework (Wiltsey Stirman et al Imp Sci 2019)
Compatibility (appropriateness)	Extent to which an intervention fits with the mission, priorities, and values of organisations or settings	Stakeholders focus groups
Culture	Organisations' norms, values, and basic assumptions around selected health outcomes	Stakeholders focus groups
Complexity	Perceptions among the delivery team that a given intervention is relatively difficult to understand and use; number of different intervention components	Qualitative interviews/ focus groups with delivery team
Self-efficacy	Delivery team's belief in its ability to execute courses of action to achieve implementation goals	N/A
Potential for Scale-up	The scalability (the ability of a health intervention shown to be efficacious on a small scale and/or under	Intervention Scalability Assessment Tool (ISAT) 

	controlled conditions to be expanded under real world conditions to reach a greater proportion of the eligible population while retaining effectiveness [Milat et al 2013]) of a discrete health program or intervention	
--	--	--

## **6.5 Participant Withdrawal**

### **6.5.1 Reasons for withdrawal**

Possible reasons for participants to withdraw from the study may include illness, death, competing priorities, or simply no longer wishing to participate.

### **6.5.2 Handling of withdrawals and losses to follow-up**

The Participant Information Sheet (PIS) and consent form will clearly state that participants are free to withdraw from the study at any time without affecting their future relationships with the researchers or organisations involved with this study. If participants decide to withdraw from the study, we will not collect any further information from them. Any information that we have already collected, however, will be kept and may be included in the study results. Participants will be assured that their decision will not have any impact on current or future relationship with the researchers at the University of Sydney or any other organisations associated with this study. To ensure a complete data set as possible, the study team will make every reasonable effort to contact and complete follow-up outcomes of every enrolled participant, including those who deviate from the intervention protocol. Attempts will be made to ensure all outcomes will be collected. At a minimum and only as a last resort, we will attempt to collect the primary outcome. Where possible, we will record the reason for loss to follow-up (e.g. consent withdrawn).

### **6.5.3 Replacements**

Replacements for withdrawn participants will not be made. The sample size calculation assumed a dropout rate of 20%, which is higher than the expected drop-out rate, so we are confident that replacement of withdrawn participants will not be necessary to maintain study power.

## **6.6 Trial Closure**

Participants will be followed up for 6 months after randomisation. Intervention group participants who consent to the additional follow-up measurement will be followed up for 12 months after

randomisation. Adverse events such as exercise related falls, musculoskeletal injury or cardiovascular events will be monitored by questions in the monthly health diaries..

## **7. STATISTICAL METHODS**

### **7.1 Sample Size**

A sample size of 1000 people (500/group) will provide 90% power to detect a between-group difference of 1000 steps/day (SD 4200), assuming 25% dropouts, alpha 5%. The sample size calculation was undertaken using the `sampsi` command in Stata.

### **7.2 Statistical Analysis**

Analyses will be guided by a rigorous statistical analysis plan developed a priori as we have done previously and use an intention-to-treat approach. The primary outcome will be analysed using generalised linear regression to assess the effect of group allocation, with its corresponding baseline score as a covariate. Continuous secondary outcomes will be analysed using linear regression adjusting for the corresponding baseline measure of the outcome variable as appropriate. We will use log-binomial regression to determine the between-group difference in the proportion of people increasing daily steps by 2000+. Fall rates will be analysed using negative binomial regression models to estimate the difference in rates between groups after 6 and 12 months with exploratory analyses adjusting for amount of physical activity. There will also be pre-defined subgroup analyses included by age, rurality/remoteness of residence, number of medical conditions and baseline fall history. Analyses will be conducted using Stata 14 software.

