
Study Procedures
	
Trial participants will be recruited via advertisements in community newsletters, websites and mainstream and social media, and through research volunteer registries, community organisations and health promotion services targeting women. After telephone screening for eligibility and upon giving informed consent, participants will complete a baseline survey including questions about general health and surveys related to secondary outcomes. They will wear an accelerometer device (ActiGraph) over 7 days to determine their baseline physical activity including average daily step count. They will then be randomly allocated to either the intervention group, (n=500), or a waitlist control group, (n=500). Participants will complete a similar survey at 6 months post-randomisation and will wear the accelerometer again at 6 months post-randomisation for 7 days to determine end of program daily step count and physical activity. . Intervention participants will be invited to extend their participation in the study for a further 6 months to complete a similar survey and wear the accelerometer again at 12-months post-randomisation to determine daily step count and physical activity maintenance. Completion of this extra follow-up will be optional.
 
The intervention group will receive access to Active Women over 50 program, which includes telephone health coaching, email or SMS motivational messages incorporating several behaviour change techniques (BCTs), a program-specific website and a private Facebook page to support their physical activity. The control group will be waitlisted to receive the Active Women over 50 program after completing all 6-month follow-up measures.

Statistical Procedures Analysis Plan Sample Size
	
Analysis Plan
 
The primary outcome will be analysed using generalised linear regression to assess the effect of group allocation at 6 and 12 months, with its corresponding baseline score as a covariate. Continuous secondary outcomes will be analysed using linear regression, adjusting for the corresponding baseline measure of the outcome variable as appropriate. We will use log-binomial regression to determine the between-group difference in the proportion of people increasing daily steps by 2000+. Fall rates will be analysed using negative binomial regression models to estimate the difference in rates between groups after 6 months. There

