Moreover, 62% of women in this age group live with at least one chronic condition. There are personal, cultural and structural barriers to physical activity for women in this age group. The onset of menopause can bring physical changes (such as hot flushes, weight gain and fatigue) that are barriers to being active. Women may be aware of the benefits physical activity can have on these symptoms and bodily changes but may perceive negative attitudes while exercising in public. Women in regional and remote areas may face additional barriers due to geography and access to physical activity opportunities and services. The competing demands and specific barriers to exercise that middle-aged women experience necessitate targeted support to encourage the adoption and maintenance of regular physical activity for healthy ageing.

Our previous systematic review demonstrates the beneficial effects of health coaching. Health coaching had a small, statistically significant effect on physical activity. However, there was no evidence of an effect of health coaching on mobility, quality of life, and mood, suggesting that, to address all project objectives, health coaching should be combined with other approaches, such as online information provision, or social support. Health promotion interventions that aim to change lifestyle behaviours, which are delivered by digital technologies, offer an efficient, effective, and scalable solution for preventing noncommunicable diseases and addressing physical inactivity. Community members are now generally savvy digital service users thanks to COVID-19. The virtual, technology-driven design of this research supports rapid, implementation nationwide, including rural/regional Australia, and helps address the time challenges experienced by many women due to competing pressures.

We developed and pilot-tested the Active Women over 50 program among 62 women aged 50+ years. Our pilot process and impact evaluation results demonstrated high acceptability and uptake. The intervention participants increased daily steps from baseline by 2000+ steps (OR 6.31, 95%CI: 1.22 to 32.70), and increased their overall physical activity levels (light, moderate, and vigorous intensities) more than controls. The high uptake, engagement, positive recommendation (87% would

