## **4 STUDY DESIGN**

### **4.1 Type of Study and Participants**

This study will use a two-arm parallel pragmatic hybrid type I effectiveness-implementation randomised controlled trial (n=1000) to test the effectiveness of the Active Women over 50 program on daily steps at 6 months compared with wait-list control among women aged 50+. In addition, a process evaluation will be undertaken to explore the experiences of participants in the intervention group after completing the program through interviews of approximately 30 participants and the impressions survey completed by all intervention group participants at 6-month follow-up. An economic analysis will also be carried out to evaluate cost-effectiveness, considering the perspective of both healthcare providers and community funders. The impact of the Active Women over 50 program on physical activity and secondary outcomes, 6 months after the program has ended, will be evaluated for intervention group participants 12 months after randomisation.

Participants will be randomly allocated in equal numbers to:

- a) Immediate participation in the 6-month Active Women over 50 program (intervention group), n=500 or
- b) Delayed participation in the Active Women over 50 program, waitlist control (control group, n=500)

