#### **5.5 Enrolment and Randomisation Procedures**

Participants will be enrolled into the study after initial screening to determine their suitability has been completed over the telephone, and having provided informed consent and completed all baseline surveys and device-based measurement of physical activity. Each participant will receive a study enrolment number, and this will be documented on all study documents. Group allocation will be determined using REDCap (Research Electronic Data Capture), a centralised web-based randomisation system within The University of Sydney with randomly permuted block sizes of four stratified by rural and urban locations. This will ensure concealment of allocation to groups and an auditable process.

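### Randomisation is stratified by rural/urban location, but the stated primary model adjusts for baseline steps only; if location predicts steps beyond baseline, the standard error is slightly too large

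*Protocol*

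**What the plan says.** Section 5.5 of the protocol sets allocation by "randomly permuted block sizes of four stratified by rural and urban locations", and section 4.1 makes it 1:1.

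Section 7.2 states that the primary outcome will be "analysed using generalised linear regression to assess the effect of group allocation, with its corresponding baseline score as a covariate". The synopsis (Statistical Procedures) names the same covariate: "to assess the effect of group allocation at 6 and 12 months, with its corresponding baseline score as a covariate". Neither place mentions the stratum.

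For the other outcomes, section 7.2 adjusts the continuous secondary outcomes for their own baseline values. It names no covariate for the log-binomial model or for the main negative binomial model; physical activity enters the falls model only in exploratory analyses.

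Location has one role in the analysis, as a subgroup factor in section 7.2: "pre-defined subgroup analyses included by age, rurality/remoteness of residence, number of medical conditions and baseline fall history". The subgroup list in the synopsis leaves it out.

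**The concern.** Stratified blocks of four keep the arms within two participants of each other in each stratum at randomisation. If rural and urban women differ in 6-month steps, that balance lowers the true variance of the treatment estimate. A model without the stratum does not register this: the between-stratum variation stays in the residual, and the reported standard error exceeds the actual one.

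The protocol gives some reason to expect such a difference. It chose location as its only stratification factor, makes it a subgroup, and says in section 2.1: "Women in regional and remote areas may face additional barriers due to geography and access to physical activity opportunities and services". That support is qualitative.

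At stake are a slightly wide confidence interval and a slightly conservative p-value for the primary comparison.

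**Working it through.** **Reproducing the stated sample size.** Section 7.1 gives a difference of 1000 steps/day, SD 4200, 90% power, alpha 5% (taken as two-sided), 25% dropout and N = 1000.

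- Per arm: 2 × (1.960 + 1.282)² × 4200² / 1000² = 371.
- With dropout: 371 / 0.75 = 495 per arm, 990 in total, which agrees with 1000.
- With 375 completers per arm (500 × 0.75): SE = 4200 × √(2/375) = 306.7, and power = Φ(1000/306.7 − 1.960) = 90.3%.

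This uses no covariates, so the planned size does not depend on the point at issue.

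**Effect of leaving the stratum out.** Let p be the rural share, d the rural-urban difference in 6-month steps given baseline steps, and ρ the correlation of baseline with 6-month steps. The protocol gives none of these. Assumed ranges: p 0.25-0.5, d 0-2000, ρ 0-0.7.

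- Share of residual variance due to stratum: R² = p(1−p)d² / [4200²(1−ρ²)].
- Inflation of the model SE: 1/√(1−R²).
- Type I error of the test without the stratum: 2 × [1 − Φ(1.960 × inflation)].

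Worked ends of the range:

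- p = 0.25, d = 500, ρ = 0: R² = 46,875 / 17,640,000 = 0.0027; inflation 0.13%.
- p = 0.5, d = 1000, ρ = 0.7: R² = 250,000 / 8,996,400 = 0.0278; inflation 1.42%.

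| d (steps/day, given baseline) | SE inflation | Type I error without stratum | Power with stratum, ρ = 0 (90.3% without) |
|---|---|---|---|
| 0 | 0% | 0.050 | 90.3% |
| 500 | 0.1-0.4% | 0.049-0.050 | 90.4% |
| 1000 | 0.5-1.4% | 0.047-0.049 | 90.6-90.7% |
| 2000 (extreme) | 2.2-6.1% | 0.038-0.045 | 91.5-91.9% |

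The power column overstates the gain, because the 90.3% treats the model SE as the true SD. At p = 0.5, d = 1000, ρ = 0, the estimate already has SD 304.5 under balanced allocation, so the model without the stratum has power Φ[(1000 − 1.960 × 306.7)/304.5] = Φ(1.310) = 90.5%, against 90.7% with it.

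**Simulation check.** Stratified blocks of four, 750 participants without dropout, p = 0.3, ρ = 0.5, 3000 runs per scenario.

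| d | Mean model SE without / with stratum | SD of the estimate without / with stratum | Type I error without / with stratum |
|---|---|---|---|
| 500 | 265.7 / 265.2 | 263.3 / 263.3 | 0.048 / 0.049 |
| 1000 | 265.7 / 263.6 | 267.9 / 267.9 | 0.051 / 0.054 |
| 2000 | 265.6 / 257.1 | 256.3 / 256.2 | 0.042 / 0.049 |

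Mean bias was within simulation error of zero throughout. The Monte Carlo error of a rejection rate is √(0.05 × 0.95/3000) = 0.004, so the rates at 500 and 1000 steps cannot be told apart from 0.05 or from each other. Only the extreme scenario shows the conservatism clearly. Random dropout would loosen the balance among completers and bring the rates nearer to 0.05.

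**The case against.** The strongest objection is that a full covariate list belongs in the statistical analysis plan. Section 7.2 announces such a plan, it is not shown, and naming the baseline score does not exclude other covariates. This has weight: if that plan includes the stratum, the analysis is already right. It does not remove the point, because the protocol is not silent here. It states the covariate for the primary model in two places, and that model does not follow the stated randomisation.

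A second objection stands in full. The standard error is too large only if location adds to the prediction after baseline steps. Barriers that already act at baseline show up in the baseline count, which is adjusted for.

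A reader might also infer more than the protocol supports:

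- *That the primary result would be biased or its type I error inflated.* It would not; any error is on the conservative side.
- *That the precision gained by stratifying is lost.* The estimate keeps it. In the simulation at 2000 steps its SD was 256 with or without the stratum term; only the reported standard error was high.
- *That all the secondary models share the fault.* The log-binomial and main negative binomial models have no stated covariates to correct, and the calculation above applies to linear regression.
- *That the loss is material.* Inflation above about 2% needs a conditional gap of around 2000 steps/day, twice the trial's target effect, and nothing in the protocol points to a gap of that size.

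**Conclusion.** The point holds as a minor one about the primary model, and by the same reasoning about the linear models for continuous secondary outcomes. Under the assumed ranges for rural share and baseline correlation, the standard error is unaffected if location adds nothing beyond baseline, and is about 0.1-1.4% too large for conditional differences of 500-1000 steps/day. Over that range the type I error stays between 0.047 and 0.050, and power changes by about 0.4 percentage points or less. The sample size is unaffected, and no conclusion of the trial is likely to turn on this.

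**What to change.** In section 7.2 and in the synopsis, add the rural/urban stratum, coded as in the REDCap randomisation, as a fixed covariate beside the baseline score in the primary model. Do the same in the linear models for continuous secondary outcomes compared between groups.

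The log-binomial and negative binomial models may take the stratum too for consistency. Convergence of the log-binomial model should then be checked.

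The cost is one binary covariate that is recorded for every participant before allocation, and one degree of freedom with about 750 completers. If the statistical analysis plan already includes the stratum, only the protocol wording needs to be brought into line.

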**Table 2: Study secondary outcomes and measures**

Secondary effectiveness outcomes	Measure
Self-reported physical activity	Single-item physical activity question (In the past week, on how many days have you done a total of 30 minutes or more of physical activity, which was enough to raise your

	
breathing rate. This may include sport, exercise, and brisk walking or cycling for recreation or to get to and from places, but should not include housework or physical activity that may be part of your job”)
 
Frequency of participation in strength training and balance training

Falls rate	Monthly falls calendar
Mental wellbeing	Warwick-Edinburgh Mental Well-being Scale 
Physical function	PROMIS SF v2.0 – Physical Function 4a
Quality of life	EuroQol EQ-5D-5L 
Bodily pain	PROMIS SF v2.0 – Pain interference and Pain intensity 4a
Sleep	Pittsburgh Sleep Quality Index (PSQI) 
Balance	Perception of balance: (“Do you feel your balance is excellent, very good, good, fair, poor”)
Menopause symptoms	The Menopause-Specific Quality of Life Questionnaire
Fear of falling	(“Are you afraid of falling? (1 = not at all, 2 = little bit, 3 = moderately, 4 = quite a lot, 5 = extremely”)
Proportion achieving light physical activity and lower limit MVPA/week	Actigraph accelerometer
Proportion of people who increase their daily steps by 2000+ from baseline to 6 and baseline to 12 months after randomisation	Actigraph accelerometer
The average number of daily steps at 12 months after randomisation	ActiGraph accelerometer
Action Planning and Coping Planning	Action Planning and Coping Planning questionnaire 
Individualised goal attainment	Goal Attainment Scale at 6 months after randomisation

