### **7.3 Economic evaluation**

Economic evaluation will take a health and community care funder perspective and will aim to establish the cost-effectiveness and cost-utility of the Active Women over 50 intervention compared to waitlist control. We will calculate intervention delivery costs and community services and health service utilisation costs during the trial period for both groups. Using mean costs and mean health outcomes in each trial arm, the incremental cost per 1) additional person increasing physical activity by 2000+ steps/day, 2) additional fall prevented, 3) additional person achieving a meaningful improvement in physical function, and 4) quality-adjusted life years (QALY) gained of the intervention group compared with control group, will be calculated. Bootstrapping will estimate a distribution around costs and health outcomes and will be used to calculate the confidence intervals around the

incremental cost-effectiveness ratios. The results will be plotted on the cost-effectiveness plane, and as cost-effectiveness acceptability curves.

A range of additional sensitivity analyses will be conducted to determine the impact on the ICER of various assumptions within the economic evaluation, such as different costing methods and strategies for handling missing data.

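### The 2000+ step responder analysis names no baseline adjustment and leaves its effect measure open; a standardised logistic model would fix both at almost no cost

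*Protocol*

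**What the plan says.** Protocol section 7.2 gives the analysis of each outcome type in turn.

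- Primary outcome: a regression "to assess the effect of group allocation, with its corresponding baseline score as a covariate".
- Continuous secondary outcomes: "linear regression adjusting for the corresponding baseline measure of the outcome variable as appropriate".
- Responder outcome: "We will use log-binomial regression to determine the between-group difference in the proportion of people increasing daily steps by 2000" or more. No covariate is named. The synopsis repeats this sentence.
- Falls: "negative binomial regression models to estimate the difference in rates between groups".

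Table 2 defines the responder outcome as a change from baseline: "Proportion of people who increase their daily steps by 2000+ from baseline to 6 and baseline to 12 months after randomisation". Only the intervention group is followed to 12 months, so the randomised comparison is the one at 6 months.

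Section 5.5 stratifies randomisation by rural and urban location. Section 7.3 uses the responder outcome for a cost per "additional person increasing physical activity by 2000+ steps/day", calculated from mean costs and mean outcomes in each arm. Section 7.2 also says: "Analyses will be guided by a rigorous statistical analysis plan developed a priori". That plan is not at hand.

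**The concern.** Two things stand out in the responder sentence.

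**Baseline steps.** Every participant has a baseline accelerometer reading before randomisation, and section 7.2 uses it for the primary outcome. For an outcome defined as a rise from baseline, the baseline value is the obvious predictor: through regression to the mean, women who start low are more likely to rise by 2000 steps than women who start high. It is nevertheless the one step-based outcome with a named model and no named baseline term. Some precision that costs nothing is left unused.

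**Effect measure.** The text promises a difference in proportions. The group coefficient of a log-binomial model is the log of a ratio of proportions. These are different numbers, and the sentence does not say which will be reported.

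At stake is the precision and clarity of one secondary result. The primary analysis is unaffected.

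**Working it through.** **1. The plan's own figure.** Inputs from section 7.1: difference 1000 steps, SD 4200, 90% power, alpha 5% (two-sided assumed), 25% dropout.

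n per arm = 2 × (1.960 + 1.282)² × 4200² / 1000² = 371. Divided by 0.75 this is 495 per arm, or 990 in total, against the planned 1000. With 500 × 0.75 = 375 completers per arm, power is 90.3%. The figure reproduces, and 375 per arm is used below. (Section 6.5.3 gives dropout as 20%, a separate matter that does not change this point.) The protocol gives no power figure for the responder outcome.

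**2. Size of the responder effect.** Assume normal steps with SD 4200 at both times, a 1000-step shift and correlation r between baseline and 6 months. The documents do not give r or the shape of the distribution. The SD of change is 4200 × √(2(1 − r)). The control proportion is 1 − Φ(2000/SD of change), and the intervention proportion is 1 − Φ(1000/SD of change).

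| r | SD of change | Control | Intervention | Ratio | Difference |
|---|---|---|---|---|---|
| 0.4 | 4601 | 33.2% | 41.4% | 1.25 | 8.2 points |
| 0.5 | 4200 | 31.7% | 40.6% | 1.28 | 8.9 points |
| 0.7 | 3253 | 26.9% | 37.9% | 1.41 | 11.0 points |

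**3. What the model as written delivers.** With group as the only predictor, exp(b0) is the control proportion and exp(b0 + b1) the intervention proportion. Both arm proportions are reproduced exactly, so the difference is exp(b0) × (exp(b1) − 1). At r = 0.5 this is 0.317 × 0.281 = 0.089. The ratio is the direct output and the difference follows from the same fit. In 400 simulated trials per scenario, the group-only model fitted every time.

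**4. What adjustment gains, normal steps.** The correlation of baseline with change is −√((1 − r)/2): −0.55 at r = 0.4, −0.50 at r = 0.5 and −0.32 at r = 0.8. Baseline is therefore informative, less so as r rises. In 1000 simulated trials per value of r:

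| r | Variance ratio, adjusted/unadjusted risk difference | Power, unadjusted | Power, adjusted | Gain (points) |
|---|---|---|---|---|
| 0.4 | 0.84 | 63.1% | 70.6% | 7.5 |
| 0.5 | 0.86 | 71.3% | 78.9% | 7.6 |
| 0.6 | 0.86 | 79.9% | 84.6% | 4.7 |
| 0.7 | 0.93 | 89.9% | 92.8% | 2.9 |
| 0.8 | 0.95 | 97.6% | 98.2% | 0.6 |

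Hand check at r = 0.5: the unadjusted standard error is √[(0.317 × 0.683 + 0.406 × 0.594)/375] = 0.0349, so z = 0.0889/0.0349 = 2.55 and power = Φ(2.55 − 1.96) = 72%. Multiplying the variance by 0.86 gives a standard error of 0.0324, z = 2.74 and power 78%. Both agree with the simulation.

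**5. What adjustment gains, other shapes.** Normal steps with mean 7000 (assumed) and SD 4200 put Φ(−7000/4200) = 4.8% of women below zero steps, so the table in step 4 is favourable to adjustment. Over all the runs made, the variance of the risk difference falls by about 3-23% with normal steps and about 0-4% with right-skewed (lognormal) steps of the same mean and SD. Power rises by about 0-9 and 0-3 points respectively.

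**6. Whether log-binomial regression could carry the covariate.** Share of simulated trials without a valid fit once baseline steps are added:

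- Normal steps, SD 4200, no floor: 99.7% at r = 0.4, 98.0% at 0.5, 89.9% at 0.6, 70.2% at 0.7, 37.8% at 0.8.
- Normal steps, SD 4200, baseline floored at 300 steps: 13% at r = 0.5, falling to 0% at 0.8. With an assumed SD of 3000: 48% at r = 0.6 and 23% at 0.7.
- Lognormal steps, SD 4200: from 0% to about a third, depending on r and on the starting values given to the software.

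The range runs from near 0% to near 100%, and nothing in the protocol narrows it.

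**The case against.** The case for leaving the text alone is strong on several points, and most of it stands.

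- **The unadjusted analysis is valid.** Randomisation makes the group-only comparison unbiased, and that model fits. A reader might infer that omitting baseline steps biases the result through regression to the mean. It does not: regression to the mean acts equally on both arms.
- **The wording is probably loose, not wrong.** A reader might infer that the named model cannot deliver the stated quantity. The same paragraph uses "negative binomial regression models to estimate the difference in rates between groups" for another log-link model, so difference seems to mean comparison, and step 3 shows that the absolute difference follows from the fit. What remains is that the reported measure is not stated.
- **Sections 7.2 and 7.3 do not conflict.** A reader might infer that a ratio in 7.2 cannot feed a cost per additional responder in 7.3. Section 7.3 works from arm means with bootstrapping, which give the absolute difference without using the log-binomial coefficient.
- **Non-convergence is not a defect of the plan as written.** It arises only if baseline steps are added. The highest failure rates need normal steps that include negative counts, so the statement that the model will often not fit is unsupported.
- **A statistical analysis plan may settle this.** Covariates for a secondary binary outcome are commonly specified there, and the protocol is silent on them, not prohibitive. That is why the point is an improvement and not a finding of error.

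What the objection leaves is a modest gain in precision from data already collected, and a clearer statement of the effect measure, at almost no cost.

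**Conclusion.** The point holds as a low-cost improvement to a secondary analysis, not as an error. Section 7.2 names baseline adjustment for the primary and continuous secondary outcomes, but not for a responder outcome that is itself a change from baseline, and it does not fix whether a ratio or a difference is reported.

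The expected gain is small: about 0-4% less variance and 0-3 points of power with right-skewed steps, and about 3-23% and 0-9 points with normal steps. Real step counts cannot be negative, so the normal-theory gains are best read as an upper end. These figures rest on SD 4200, a 1000-step effect and 375 completers per arm from section 7.1, and on an assumed mean of 7000, correlation of 0.4-0.8 and distribution shape.

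If baseline steps are added, log-binomial regression may or may not fit. That is a reason to prefer another model when adjusting. It is not a criticism of the group-only model.

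**What to change.** Replace the responder sentence in section 7.2 and in the synopsis, or specify in the statistical analysis plan before unblinding, wording such as: *The proportion of participants increasing daily steps by at least 2000 from baseline to 6 months will be compared between groups by logistic regression adjusted for baseline daily steps and rural/urban stratum. The standardised (marginal) risk difference and risk ratio will be reported with robust 95% confidence intervals.*

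Modified Poisson regression with robust standard errors and the same covariates is acceptable for the ratio. In Stata, the standardised estimates come from the margins command after the logistic fit.

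Section 7.3 needs no correction on this account.

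The cost is one sentence and a few lines of code, with no new data and no change to sample size. The only downside is departing from the model now named, so the change should be dated and made before outcome data are seen by group.
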